8.3.1 Primary outcome analysis

Not applicable to this pilot and feasibility RCT.

8.3.2 Secondary outcome analysis

Not applicable to this pilot and feasibility RCT.

8.4 Subgroup analyses

There are no planned subgroup analyses in this pilot and feasibility RCT.

8.5 Interim analysis and criteria for the premature termination of the trial

Not applicable to this pilot and feasibility RCT

8.6 Procedure(s) to account for missing or spurious data

As this is an external pilot and feasibility RCT we will report the amount of missing/spurious data across all outcome measures and CRF items. Missing data within individual items of composite tools will be dealt with according to validated-scoring recommendations for those measures if indicated (or otherwise, dealt with using reasonable Keele CTU rules which will be outlined in the data analysis plan). A statistical review will be undertaken to assess the relationship between missingness at follow up (the most likely source of missing data) and baseline variables: in the event of strong associations being observed that indicate a missing at random pattern this will usefully inform the data analysis plan for a main trial.

8.7 Economic evaluation

A formal economic analysis will not be undertaken in this pilot and feasibility RCT. Health Care Resource Use data will be collected within the three and six month questionnaires and completion and response rates analysed to assess the feasibility of undertaking a full economic evaluation in a future main trial.

9 DATA HANDLING

9.1 Data collection tools and source document identification

Self-report questionnaires and clinical data collected on study specific CRFs and audio-recordings and screening logs will form the basis of the data collection. All data collected during the course of the study will be kept strictly confidential and will be handled and stored in line with the local NHS and Keele CTU Data Security procedures and Keele University's Health and Social Care Quality Management System's Standard Operating Procedures (HSCR QMS SOPs), which are in accordance with the relevant Data Protection regulations and good practice guidelines.

Study data will be recorded by clinicians or local research staff who are taking part in the study and will be trained in accordance with the protocol on completing CRFs. Originals will be retained at site and copies securely sent to Keele CTU at Keele University. Other than the Participant Contact CRF and consent form, which will contain the participant's details to allow contact for follow-up by Keele CTU, only the participant's pseudo-anonymised data will be included on CRFs. Questionnaires will include

the participant's Study ID plus date of birth and gender. The study site is responsible for redacting all other personal identifiable data prior to CRFs and any other reports being sent to Keele CTU. Following receipt, Keele CTU will contact the site to resolve any missing or discrepant data queries relating to clinical data in accordance with Keele CTU procedures

9.2 Data handling and record keeping

Data management is by Keele CTU. Audit of data entry is undertaken for questionnaires and CRFs by Keele CTU following HSCR QMS SOPs and the verification checks supported by the research team. For details on data protection systems, see Section 11.5.

9.3 Access to Data

The research team will receive anonymised datasets for purpose of data reporting to the TMG and TSC and at the end of follow up for final data cleaning/checking and end-of-study analysis. All identifiable data will be retained within the Keele CTU-secure network drives and at local sites in line with NHS information Governance policies.

9.4 Data Sharing Agreements

Prior to the start of recruitment, a signed Organisation Information Document and model non-commercial trials agreement (mNCA) will be in place between each hospital site, and Keele University to ensure the safe and lawful process of data sharing across organisations. A service level agreement, including data sharing agreement, will be in place between Derby CTU and Keele University to ensure the safe and lawful process of service provision and data sharing across the organisations. Derby CTU will not have access to personally identifiable data for the purpose of randomisation. Audio files containing qualitative data will be securely shared with a professional UK based transcription company under the terms of a confidentiality and data sharing agreement.

The EQ-5D-5L will be used with permission from EuroQol under the terms of its Non-Commercial Research Licence. Similarly, the OSS will be used with permission from the developers.

9.5 Archiving

At the end of the trial, data will be securely archived in line with the Sponsor's procedures for 10 years after submission of the End of Study Declaration. Data held by Keele CTU will be archived in the designated Keele CTU archive facility and site data and documents will be archived at the participating sites. Following a retention review, if the archived material is agreed to be destroyed, arrangements for confidential destruction will then be made.

10 MONITORING & AUDIT

10.1 Study Management

Trial Sponsor: Keele University as the sponsor is responsible for trial initiation, management and financial management of the trial. These functions are devolved to Keele CTU as will be detailed in the Delegation of Sponsorship Functions agreement, as follows:

Chief Investigator (CI): The CI (CL) is also the NIHR Post-Doctoral Fellowship holder and will lead the design, conduct, co-ordination and management of the study. The CI has overall responsibility for the scientific quality and delivery of the study. The CI will also be responsible for safety reporting and escalation of reportable adverse events.

CTU: The Trial Sponsor delegates the management of the trial to Keele CTU. Keele CTU will provide set-up and monitoring of trial conduct to Keele University's HSCR QMS SOPs, and the GCP Conditions and Principles as detailed in GCP standards. In addition, Keele CTU will provide support in obtaining research ethics and governance approvals and clinical site set-up, ongoing management including training, monitoring reports and promotion of the trial. In association with the CI, Keele CTU will support the day-to-day running of the trial including some help with trial management and administration, data management, and safety reporting. Regular monitoring of study recruitment will be performed and intervention CRFs will be audited against the clinical records by clinical site PI's or their designate, for completion accuracy.

Derby CTU will provide and manage the randomisation system for the SPeEDy RCT.

NIHR Clinical Research Networks: The West Midlands CRN will co-ordinate CRN support across the recruiting sites and together with other CRNs will provide funding or staff resource to secure the additional clinical time associated with service support to embed the study into the sites to allow identification and recruitment of eligible participants.

Clinical Site PIs: The clinical site PIs will be responsible for the conduct of the trial at their site as detailed in the applicable Sponsor-Site Agreement available in the Study Site File and ensuring the trial is run at their site in accordance with the GCP Conditions. This includes (but is not limited to), ensuring GCP training for those undertaking consent, completion of relevant CRFs, delivery of intervention, care of the patients and safety reporting.

Trial Management Group (TMG): The CI is responsible for the conduct of the trial and will convene the TMG. The TMG will comprise members of the research team and Keele CTU and will have overall responsibility for the clinical set-up, ongoing management and monitoring, promotion of the trial, and for analysis and interpretation of results. The CI will chair the TMG to oversee; (i) the protocol delivery, (ii) CRF development, (iii) obtaining approval from the HRA and agreements with sites, (iv) completing cost estimates and project initiation, (v) nominating members for, and facilitating, the TSC, (vi) monitoring of screening, recruitment, treatment and follow-up procedures, (vii) data collection, and database

development, (viii) reporting annually to the REC. The TMG will meet on a regular basis throughout the study.

10.1.1 Trial Steering Committee (TSC) members

An independent TSC has been appointed in line with Keele University's HSCR QMS SOPs (see list of members under key contacts Page 6) and will provide overall supervision of the study, in particular study progress, adherence to protocol, participant safety and consideration of new information relevant to the research question(s) or design. It includes an Independent Chair and four other independent members, including a statistician (1), lay representatives (2) and clinical representatives (2). The CI, senior statistician and Trial Manager will attend the TSC meetings and present and report progress. The TSC will meet initially to approve the protocol prior to submission for Health Research Authority approval and then at agreed time points over the duration of the trial. Since this is a pilot trial with no planned interim statistical analysis, a Data Monitoring Committee will not be formed and the TSC will take responsibility for reviewing the safety of the trial including advice regarding progression to a main RCT with reference to the pre-specified progression criteria.

10.2 Monitoring arrangements

Monitoring will be conducted by the TMG based on the trial risk assessment and in accordance with Keele University's HSCR QMS SOPs, and agreed by the TSC. Monitoring will also be undertaken by the approving Research Ethics Committee (REC) in the format of annual progress reports and the funder in the format of progress reports as required by the NIHR Post-Doctoral Fellowship scheme.

10.3 Auditing procedures

Completeness of consent forms and baseline questionnaires will be audited by the research team and Keele CTU. Clinical case notes will be audited by the clinical site PI, or delegate, with reference to the trial interventions as a means of contributing to the assessment of intervention fidelity.

10.4 Safety Reporting

Adverse events

A Serious Adverse Event (SAE) is defined by the Health Research Authority (HRA) as an untoward occurrence that: (a) results in death; (b) is life-threatening; (c) requires hospitalisation or prolongation of existing hospitalisation; (d) results in persistent or significant disability or incapacity; (e) consists of a congenital anomaly or birth defect; or (f) is otherwise considered medically significant by the investigator.

In the context of the SPeEDy study, expected SAEs include re-rupture or failure to heal of the repaired rotator cuff tendon(s), and participants allocated to physiotherapist-led exercise subsequently undergoing surgery to repair their rotator cuff.

A SAE occurring to a research participant must be reported to the REC where in the opinion of the CI the event was: “Related” that is, it resulted from administration of any of the research procedures, and/ or “Unexpected” that is, the type of event that is not an expected occurrence as a result of the intervention provided.

In addition to participant self-report, we will ask study clinicians including orthopaedic surgeons and physiotherapists to report all related and/or unexpected adverse events and SAEs if they become aware of them during the trial, with the exception of non-trial related prolongation of the existing hospital stay or planned hospitalisations. Similarly, if the participant’s GP becomes aware that a SAE has occurred we will request that this is reported, as detailed in the letter informing them that their patient is participating in the study. Reporting procedures will be made clear during the protocol study training and will be contained in site files for all clinicians involved in the study. We will also ask participants to report any adverse events they have experienced due to their participation in the trial in their three and six month questionnaires.

Once a SAE is identified and reported, this information will be passed to the Trial Manager who will ensure that the necessary paperwork is completed and inform the CI. In line with Keele University’s HSCR QMS SOPs the reporting clinician is to give their assessment and the CI will assess whether the event is related to or resulted from any of the trial procedures or interventions and expectedness, according to the process laid out in Keele University’s HSCR QMS SOPs. Any SAE considered to be related to the trial procedures and/ or unexpected will be reported to the Sponsor, REC and the TSC Chair by the CI within 15 days of becoming aware of the event. SAEs occurring later than six months post randomisation do not need reporting.

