3 OBJECTIVES AND OUTCOME MEASURES/ENDPOINTS

3.1 Primary objective

In adult patients diagnosed with traumatic tears of the rotator cuff, is it feasible to conduct a future, substantive, multi-site RCT to test the hypothesis that physiotherapist-led exercise is not inferior to surgical repair of the rotator cuff in terms of clinical outcomes but is more cost-effective.

Objectives

- 1) Determine feasibility of recruiting patients
- 2) Determine feasibility of retaining participants
- 3) Determine zone of clinical equipoise, i.e. the range of patient characteristics (including age, size and location of rotator cuff tear, level of functioning) where clinicians are prepared to randomise or not
- 4) Determine proportion and reasons for treatment cross-over
- 5) Estimate the number of potential and willing sites for the future main trial
- 6) Identify barriers and facilitators to recruitment and retention
- 7) Determine participant satisfaction with the interventions
- 8) Determine the number and nature of adverse events.

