3.3 Outcome measures/endpoints

Feasibility outcomes:

- 1) Numbers of patients screened, number eligible, number approached, number consenting, number randomised, and number accepting allocation
- 2) Numbers of participants continuing in allocated treatment
- 3) Follow-up response rates to questionnaires at three and six months post-randomisation (including Oxford Shoulder Score and EQ-5D-5L)
- 4) Data from screening logs, including reasons for not approaching potentially eligible patients to inform determination of zone of clinical equipoise
- 5) Numbers of participants receiving treatment (surgery or PT-led exercise) other than that which was allocated to determine proportion of participants who cross-over
- 6) Feasibility of recruiting participating sites and numbers of additional sites who are interested in participating in the main trial
- 7) Participant satisfaction with the interventions on a five-point ordinal scale; Very Satisfied/Satisfied/Neutral/Dissatisfied/Very Dissatisfied
- 8) Barriers and facilitators to recruitment, retention and treatment cross-over (qualitative data; audio recording and individual interviews).

Clinical outcomes:

- 1) Pain and disability assessed using the Oxford Shoulder Score (OSS) at baseline, three and six months post-randomisation by post with telephone call for minimum data collection if no response to reminder postal questionnaire
- 2) Health related quality of life assessed using the EQ-5D-5L at baseline, three and six months post-randomisation by post with telephone call for minimum data collection if no response to reminder postal questionnaire
- 3) Days lost from work due to the shoulder problem at three and six months post-randomisation via postal questionnaire
- 4) Time taken to return to driving, if applicable, via questionnaire at three and six months post-randomisation via postal questionnaire
- 5) Number and type of adverse events for up to six months post-randomisation via patient self-report questionnaire or telephone Minimal Data Collection (MDC) at three and six months and via surgeon, physiotherapist or GP report.

Self-report data relating to further health care resource use, including NHS- and private borne service and medication costs will also be collected.

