2) Comparator; surgical repair plus usual post-operative rehabilitation. Surgical repair will be guided by the size and location of the tear and also surgeon preference, the details of which will be recorded on a specific case report form and reported accordingly. Similarly, the content of post-operative rehabilitation is variable across the UK [21] but typically begins with a period of immobilisation using an arm sling for up to six weeks. After this period, rehabilitation progresses gradually with the aim of restoring movement, strength and function. The content of the post-operative rehabilitation programme (in-patient and out-patient) will also be recorded on a case report form following case note review and reported accordingly.

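### Does naming cross-over surgery as an expected SAE in Section 10.4, under a loosely worded reporting request, leave the adverse-event results unreliable?

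*Combined protocol and SAP*

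**What the plan says.** Section 10.4 (Safety Reporting) gives the standard SAE definition, which includes hospitalisation. It then lists the expected SAEs for this trial: re-tear or non-healing after repair, and "participants allocated to physiotherapist-led exercise subsequently undergoing surgery to repair their rotator cuff". In the other arm the same operation is the allocated treatment, described in Section 4.1 as "surgical repair plus usual post-operative rehabilitation".

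Three routes bring events to the trial team:

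- Study clinicians are asked "to report all related and/or unexpected adverse events and SAEs if they become aware of them during the trial". The request is then narrowed by an exception, which is worded "with the exception of non-trial related prolongation of the existing hospital stay or planned hospitalisations".
- For general practitioners, the wording is that if the "GP becomes aware that a SAE has occurred we will request that this is reported", with no limit on type of SAE.
- Participants are asked in the questionnaires for "any adverse events they have experienced due to their participation in the trial".

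Once an SAE has been reported, Section 10.4 sends it to the Trial Manager. The chief investigator then judges relatedness and expectedness. Only SAEs judged related and/or unexpected go on to the sponsor, the ethics committee and the chair of the Trial Steering Committee (TSC).

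Objective 8 in Section 3.1 is "Determine the number and nature of adverse events". Section 3.3 separately lists, as a feasibility outcome, "Numbers of participants receiving treatment (surgery or PT-led exercise) other than that which was allocated".

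On timing, the objectives table in the Study Summary places the adverse-event questionnaires at 3 and 6 months after surgery. The Summary's follow-up row, Section 3.3 and the SAE cut-off in Section 10.4 all run to six months from randomisation.

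**The concern.** Two features of the clinician request are open on a strict reading. The words limiting it to related and/or unexpected events may or may not apply to SAEs as well as to other adverse events. If they do, a repair that is listed as expected and judged unrelated is not requested. The exception for planned admissions may or may not be limited to those unrelated to the trial. If it is not, an elective cross-over repair is exempt. The GP and participant routes have different scopes again, so in principle the same operation could enter the SAE list through one route or site and not another.

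What would be at stake is the SAE total in the exercise arm. It could mix treatment switching with harm to an unknown degree, in a trial that has adverse events as an objective and relies on the TSC for safety review without a data monitoring committee (Section 10.1.1). Section 8.1 names cross-over from exercise to surgery as the principal cross-over concern, so the event is not remote.

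The timing conflict looks like a second problem, because a clock started at surgery has no meaning for exercise participants who never have surgery.

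**Working it through.** **Inputs.** Exercise arm of 38 and a desired upper cross-over level of around 15% (Section 8.1); progression limit of under 25% cross-over (Section 8.3); median NHS wait for surgery of 74 days (Section 7.2). The plan states no SAE figure to reproduce.

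**Step 1: the possible readings, and what each does to a cross-over repair.**

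| Reading of the clinician request | Submitted as an SAE? | Counted as cross-over? |
|---|---|---|
| A. All SAEs are requested | Yes | Yes |
| B. Only related and/or unexpected SAEs are requested | Only if judged related | Yes |
| C. Any planned admission is exempt | No, by this route | Yes |

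The last column does not vary, because the cross-over outcome in Section 3.3 depends on treatment received and not on an SAE form. Section 7.8 has site staff record the date treatment commenced, and Section 10.3 has case notes audited against the trial interventions. The operation can therefore be traced without the safety route.

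**Step 2: which reading fits the rest of Section 10.4.** The chief investigator assesses expectedness after an SAE has been submitted. If clinicians had already screened out expected, unrelated SAEs (reading B), much of that step would be redundant. Under reading C, a general exception would remove an operation that the same section lists by name, and the listing would serve little purpose. Both points favour reading A, though they are inferences and not an explicit statement. An expected repair judged unrelated is not sent on to the sponsor, ethics committee or TSC chair under any of the three.

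**Step 3: the most that the SAE total could move.** Suppose every cross-over repair is submitted, compared with none:

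- At 15%: 0.15 × 38 = 5.7, about 6 events.
- At the highest count that meets the limit: 9/38 = 23.7% is under 25%, and 10/38 = 26.3% is not, so 9 events.

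These are extremes. GP or participant reports would narrow the gap.

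**Step 4: what uses that total.** The four progression criteria in Section 8.3 concern sites, recruitment, cross-over and follow-up for the Oxford Shoulder Score; none uses SAEs. Sections 8.3.1 and 8.3.2 state that primary and secondary outcome analyses do not apply. No section plans a comparison of SAE totals between arms. Section 3.3 asks for number and type, and a breakdown by type shows cross-over repair as its own category.

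**Step 5: the timing conflict.** With a month of 365.25/12 = 30.44 days, the 74-day wait is 74/30.44 = 2.43 months. Six months after surgery would then fall at 6 + 2.43 = 8.43 months after randomisation, beyond the six-month SAE cut-off, so the Summary phrase cannot be followed together with Section 10.4. It would not be followed in practice. The schedule in Section 7.8 collects adverse events at the same 3- and 6-month contacts as the Oxford Shoulder Score and EQ-5D-5L, and Section 3.3 times those contacts from randomisation.

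**The case for a change.** The strongest case for a change is that the central assessment in Section 10.4 operates only on events that have been submitted, so it cannot prove that clinicians are asked to submit them. A protocol that names an event as an SAE should leave no doubt about whether it is collected. Section 10.4 leaves procedures to training and site files, and Section 8.3 leaves analysis detail to a later plan agreed by the TSC; neither is available here. In an arm of 38, a total that can shift by 6 to 9 events is hard to interpret, and one sentence would settle the matter. The timing phrase is wrong on its face and concerns the data source for an objective.

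Part of this stands. The sentence is loose, the argument from the workflow is an inference, and the Summary phrase conflicts with the operative text. A bare SAE total for the exercise arm should not be read without its breakdown by type. What does not follow is any loss of information or effect on a conclusion. A missed SAE form can be recovered by checking the SAE list against the cross-over count. Different scopes for clinicians, GPs and participants are ordinary tailoring by source. Nothing in the documents suggests that sites would in fact diverge. Giving SAE totals both with and without cross-over repair would show nothing beyond what reporting by type and the separate cross-over count already show.

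**Conclusion.** No change to the plan follows. The clinician-reporting sentence is a gap in wording that the surrounding text and routine reconciliation fill sensibly, and the Summary's surgery-based timing is a clerical slip overridden by consistent operative sections. The largest possible effect is on a descriptive SAE total: about 6 of 38 at 15% cross-over, and 9 of 38 at the highest count within the progression limit. No progression decision uses that total, and the operations behind it are counted elsewhere.

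This rests on three assumptions: that adverse events are reported by type as Section 3.3 says, that cross-over is recorded independently of SAE forms, and that the training and site files give sites a common instruction as Section 10.4 promises. The third could not be checked. If it failed, the SAE total would vary by site within the range above, while the cross-over count would be unaffected. Which reporting rule applies is for the sponsor to settle, and nothing here alters the notifications already required.

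### The adverse event outcome carries no attribution condition, but section 10.4 collects non-serious events only through two filtered routes and words relatedness in two ways

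*Combined protocol and SAP*

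**What the plan says.** Objective 8 (section 3.1) is to "Determine the number and nature of adverse events". Clinical outcome 5 (section 3.3) is "Number and type of adverse events for up to six months post-randomisation via patient self-report questionnaire" or telephone minimum data collection (MDC), supplemented by reports from surgeons, physiotherapists and GPs. The follow-up table in section 7.8 lists adverse events at both time points, by questionnaire, MDC and clinician report. None of these places restricts the outcome to events with a particular cause.

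Section 10.4 sets out the collection rules:

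- **Participants** are asked in the three- and six-month questionnaires for "any adverse events they have experienced due to their participation in the trial".
- **Study clinicians** are asked to "report all related and/or unexpected adverse events and SAEs if they become aware of them during the trial". The one carve-out concerns time in hospital: "with the exception of non-trial related prolongation of the existing hospital stay or planned hospitalisations".
- **GPs** have an SAE-only route: if the "GP becomes aware that a SAE has occurred we will request that this is reported".

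Section 10.4 also describes relatedness twice. For reporting to the ethics committee, a related event is one where "it resulted from administration of any of the research procedures". For the chief investigator's review of a reported SAE, "the CI will assess whether the event is related to or resulted from any of the trial procedures or interventions and expectedness".

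**The concern.** The outcome is unconditional and its collection is conditional. A participant must first decide that an event was caused by being in the trial. That is a hard question to put to someone who had an operation they might well have had anyway. Section 2 says that traumatic tears are currently sent promptly for a surgical opinion, and sections 7.2 and 7.3 say that participants reach their treatment through the usual routes. Someone with a stiff shoulder after surgery could honestly answer that the trial did not cause it. Section 7.4 confirms that nobody is blinded, so the answer may depend on the arm.

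Section 1 gives surgical risk, naming infection and post-operative stiffness, as part of the argument for the trial. Section 10.1.1 states that no data monitoring committee will be formed and that the steering committee will review safety and advise on progression. If the counts leave out known complications of one treatment, that committee sees an incomplete picture and the main trial may inherit the same collection method.

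**Working it through.** No expected adverse event rate or capture rate appears in the documents, so there is no figure to reproduce. The check sets each reporting route against the outcome.

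**Step 1: what each route asks for.**

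| Route | Condition in section 10.4 | Non-serious events? |
|---|---|---|
| Participant | Must be attributed to trial participation | Yes, if attributed |
| Study clinician | Related, unexpected, or both | Yes, if the condition is met |
| GP | None | No, SAEs only |

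Two of the three routes are filtered. The GP route is not. For non-serious events only the two filtered routes remain.

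**Step 2: what the clinician filter tests.** It is not purely a test of attribution. Section 10.4 defines an unexpected event by whether its type is anticipated from the treatment given, so an unrelated but unexpected event is still reportable. The sentence also leaves open whether the qualifier applies to SAEs or only to the adverse events named before them.

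**Step 3: trace one event.** Take post-operative stiffness in a participant allocated to surgery, assumed not to meet any of the SAE criteria.

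- *Participant:* requested only if the participant blames the trial.
- *GP:* not requested, because it is not serious.
- *Clinician, unexpected?* Arguably not. Section 1 names it as a known risk of surgery.
- *Clinician, related?* This depends on the definition. If relatedness is limited to research procedures, and surgery is regarded as usual care, the event is neither related nor unexpected and is not requested. If relatedness extends to the trial interventions, surgery is a randomised arm (section 4.1), the event is related, and the clinician should report it on becoming aware of it.

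Under the narrow definition, the only remaining route is the participant's own attribution. Under the wide one, the clinician route covers the event. Neither definition is expressly given as the rule for what clinicians report: the narrow one governs which SAEs go to the ethics committee, and the wide one governs the chief investigator's assessment of SAEs already reported.

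**Step 4: scale.** With 1:1 allocation of 76 participants, each arm has 76 / 2 = 38. One affected participant is 1 / 38 = 2.6% of an arm. This shows only how much each missed participant shifts an observed proportion; it does not estimate how many would be missed.

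**The case against.** The case for leaving the plan alone has several parts.

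- **Surgery is a trial treatment.** The treating surgeon and physiotherapist are asked to report, and if they use the wider meaning of relatedness, complications of allocated surgery are covered. This stands as a reason not to say that events *will* be lost. It does not settle the matter, because the narrower meaning is in the same section.
- **The instruments are not in the documents.** The questionnaire item, MDC script and report forms may be neutrally worded. This also stands. But section 10.4 is the protocol's own statement of what participants are asked, and it says nothing about the wording used in the MDC.
- **Other data could reveal complications.** Resource use is collected in both arms (though not in the MDC), surgery and rehabilitation details are recorded on case report forms, case notes are audited, and site training covers adverse event reporting. None of the data sources is a designated adverse event route: the audit serves intervention fidelity (section 10.3), the forms record treatment content (section 4.1), and resource-use data are there to test the feasibility of an economic evaluation (section 8.7). Training passes on whatever rule is written.
- **This is a descriptive pilot.** Sections 8.3.1 and 8.3.2 plan no outcome analysis and section 8.3 has no adverse event criterion for progression. That limits the consequence but does not remove objective 8.

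A reader might go further and infer that every route filters on attribution, or that surgery will look safer than it is. The documents support neither. GPs are asked for any SAE, and expectedness is a different test from attribution. On direction, exercise participants might blame the trial more readily because it changed their pathway, but surgical participants also received their operation by allocation and could equally blame it.

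**Conclusion.** The mismatch is real and limited. The collection rules in section 10.4 are narrower than the outcome in sections 3.1 and 3.3, and the two wordings of relatedness leave it unclear whether the clinician route closes the gap. Expected, non-serious complications of surgery may be under-ascertained, possibly unequally between arms. SAEs are better protected, through the unfiltered GP request and possibly through clinicians as well.

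This rests on three assumptions: that the questionnaire item follows section 10.4, that some complications such as stiffness fall short of the SAE criteria, and that at least some clinicians would apply the narrower meaning of relatedness. Any numerical estimate of the loss would need both a complication rate and an attribution rate, and the documents give neither, so the size and direction stay open. The point is worth acting on as a cheap improvement; it does not threaten the trial's feasibility conclusions.

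**What to change.** Reconcile sections 3.3 and 10.4 by collecting first and judging cause afterwards:

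1. In the three- and six-month questionnaires and the MDC, ask both arms the same neutral question: any new health problem or complication since the last contact, whatever the cause.
2. Ask study clinicians to report adverse events in both arms on the same basis, and state whether any remaining qualifier applies to SAEs.
3. Use one definition of relatedness throughout, covering the trial interventions as well as the research procedures.
4. Have the reporting clinician and the chief investigator assign relatedness and expectedness after the event is recorded, as section 10.4 already does for SAEs.
5. Tabulate all events, and related events separately, by allocated arm and by treatment received.

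The cost is a protocol amendment, a check and if necessary a rewording of one questionnaire item and one MDC script item, and a matching change to clinician reporting instructions. The downside is more unrelated events to log and code, which should be manageable with 76 participants followed for six months.
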